Understanding the epigenomic/genomic/proteomic/environment context and regulation of metabolic phenotypes will expand our knowledge of the effects of e-cig on lung biology, and could contribute to finding successful interventions, including accurate predictions of e-cig related adverse effects. Typical omics integration methods include logistic regression or correlations among omics measurements (when measured in the same samples), intersection of gene/protein/metabolite lists (when measured in different samples), or further downstream integration by assessing alterations in pathways [309-311]. Because our omics measurements will be made in the same sample, we will be able to directly assess relationships between our molecular data through regression or correlation analyses. Of note, typical regression/correlation approaches are not appropriate for low sample numbers, and they do not readily adjust for differences in sample size between phenotype groups or for potential confounders. Another approach, which we propose here, is to directly test whether associations between miRNA or gene or cytokine and metabolite levels are specific to a group assignment. To test this, we will apply a novel linear model approach recently developed by [name] for these types of analysis:  $m = g + t + g:t$ , where  $m$  are metabolite abundances,  $g$  are miRNA or gene or cytokine levels,  $t$  is treatment group (e.g. SREC vs. continued smoking), and  $g:t$  is the interaction between miRNA or gene or cytokine level and treatment group. A statistically significant  $g:t$  interaction p-value would indicate that gene (or miRNA or cytokine):metabolite relationships are present in one treatment group and not the other. Pathway enrichment analysis of associated miRNA, genes,

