**The Effects of a Standardized Research E-Cigarette on the Human Lung:
A Clinical Trial with Bronchoscopic Biomarkers**

NCT03691350

Statistical Analysis Plan, 09/19/22

SREC SAP

The Specific Aim for this two year project is:

To assess inflammatory changes over 10 weeks (8 weeks experimental condition) for lung and urine biomarkers in smokers in a clinical trial where smokers are randomized to: continued use (n=32), complete switching to the nicotine standardized research electronic cigarette (SREC) (n=32), complete switching to the placebo SREC (n=32), or complete switching to nicotine replacement therapy (NRT) (n=32).

- 1) We will enroll 128 subjects (32 per group). For power calculations, we will use a conservatively planned 66% retention rate at 5 weeks, knowing that we have a 100% retention for never smokers receiving serial bronchoscopies. Thus, the final sample size will be 21 subjects per group (n=84). Although we expect a higher retention rate, we assume 66% to ensure that we have the minimal numbers required to reach meaningful conclusions. Since follow-up samples would not be obtained from subjects that do not finish the treatment protocol, and these samples (inflammation/omics) are our primary outcomes, we cannot use an 'intent to treat' strategy since dropouts will have missing outcome data for any analyses including follow-up measurements (the primary Aim). In light of this, we will compare dropout rates between arms and with demographic/clinical to ensure that the analyses results are not biased by unbalanced dropouts. We will also test for differences in baseline molecular measurements between subjects that dropout after baseline samples are taken vs. subjects that complete the protocol. While we will make every effort to minimize the missing data for this study, missing data can arise due to various reasons. Violation of missing completely at random (MCAR) will be checked by evaluating whether any covariates are associated with missing data. If so, these covariates will be subsequently included and controlled for in the GL(M)M models. In addition, sensitivity analyses will also be conducted using results from multiple imputation.

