Understanding the epigenomic/genomic/proteomic/environment context and regulation of metabolic phenotypes will expand our knowledge of the effects of e-cig on lung biology, and could contribute to finding successful interventions, including accurate predictions of e-cig related adverse effects. Typical omics integration methods include logistic regression or correlations among omics measurements (when measured in the same samples), intersection of gene/protein/metabolite lists (when measured in different samples), or further downstream integration by assessing alterations in pathways. Because our omics measurements will be made in the same sample, we will be able to directly assess relationships between our molecular data through regression or correlation analyses. Of note, typical regression/correlation approaches are not appropriate for low sample numbers, and they do not readily adjust for differences in sample size between phenotype groups or for potential confounders. Another approach, which we propose here, is to directly test whether associations between miRNA or gene or cytokine and metabolite levels are specific to a group assignment. To test this, we will apply a novel linear model approach recently developed by [name] for these types of analysis: $m = g + t + g:t$, where m are metabolite abundances, g are miRNA or gene or cytokine levels, t is treatment group (e.g., SREC vs. continued smoking), and g:t is the interaction between miRNA or gene or cytokine level and treatment group. A statistically significant g:t interaction p-value would indicate that gene (or miRNA or cytokine):metabolite relationships are present in one treatment group and not the

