other. Pathway enrichment analysis of associated miRNA, genes, cytokines, and metabolites (resulting from the linear models) will be performed in Ingenuity Pathway Analysis to pinpoint altered pathways and better understand how the epigenomic/genomic/proteomic/environment affects metabolic phenotypes associated with e-cig usage. Furthermore, miRNA, genes, cytokines, and metabolites involved in treatment-specific associations will be used to predict treatment group, in an effort to produce an e-cig inflammation signature. Ten-fold cross-validations of various linear-based and non-linear based machine learning methods will be tried (e.g., Random forests, naïve Bayes, Lasso) and the resulting specificity and sensitivity will be assessed to select the best performing model. Of note, the cross-validation will help ensure that the predictive models are not overfit and could be predictive on new validation data. The contribution of input molecular measurements (gene, cytokines, miRNAs, metabolites) to the model will be assessed to define the minimal set of features that yield the optimal cross-validated models.

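### A significant g:t interaction shows that the gene–metabolite slope differs between arms, not that the relationship exists in one arm and is absent from the other

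*SAP*

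**What the plan says.** Item 2 of the SAP proposes a linear model in place of ordinary correlation, in order to "directly test whether associations between miRNA or gene or cytokine and metabolite levels are specific to a group assignment". In that model, m is metabolite abundance, g is the miRNA, gene or cytokine level, and "t is treatment group (e.g., SREC vs. continued smoking), and g:t is the interaction between miRNA or gene or cytokine level and treatment group".

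The SAP then fixes the interpretation: "A statistically significant g:t interaction p-value would indicate that gene (or miRNA or cytokine):metabolite relationships are present in one treatment group and not the" other (the last word falls after a page break). The protocol, section 4.g.i (Data Analysis Plan), has the same rule: a significant term means that "relationships are present in one treatment group and not the other".

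Two steps follow. Features from these linear models go into pathway enrichment. In addition, "metabolites involved in treatment-specific associations will be used to predict treatment group, in an effort to produce an e-cig inflammation signature".

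For this analysis neither document asks for the slope within each arm, a check of its sign, or any rule that separates one-arm relationships from two-arm relationships of different strength or direction. The post hoc check in SAP item 3 concerns distributional assumptions and does not supply such a rule.

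**The concern.** The planned conclusion is presence in one group and absence in the other. The p-value addresses a different question, namely whether the two slopes are equal. Three situations make it small:

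- a relationship in one arm only;
- a relationship in both arms, in the same direction but of different strength;
- a relationship in both arms, in opposite directions.

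The plan gives all three the description that fits only the first. Biologically they differ: a link weakened or reversed after switching product is not a link that has disappeared. Because the rule stands in both documents, an analyst who follows the plan would publish statements about individual pairs that the test does not support.

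**Working it through.** **What the test tests.** Code t as 0 or 1:

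E(m) = a + b·g + c·t + d·g·t

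The slope is b in group 0 and b + d in group 1. The g:t p-value tests d = 0. It tests neither b = 0 nor b + d = 0, so it cannot by itself show that either slope is zero. This holds whatever the data.

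**Inputs for a numerical illustration.**

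- From the SAP: "Thus, the final sample size will be 21 subjects per group (n=84"). This agrees with 32 × 0.66 = 21.1.
- Not in the documents, so assumed: the true slopes, and unit SDs for g and for the residual.
- Threshold: none is stated for g:t. Two were tried: 0.05 (an assumption) and 0.0001, the one-in-10,000 rate that SAP item 3 uses for planning the primary analyses.
- The plan gives no power or effect size for this test, so there is no stated figure to reproduce.

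**Hand check at 0.05.** The standard error of d is √(1/S₀ + 1/S₁), where S is the within-arm sum of squares of g. With 21 subjects and unit SD, S is chi-square on 20 df, and the mean of 1/S is 1/18. The standard error is then about √(2/18) = 0.333. For d = 1 the ratio is 1/0.333 = 3.0. The two-sided 5% critical value on 42 − 4 = 38 df is 2.02. The chance of rejection is about Φ(3.0 − 2.02) = 0.84. Only d enters this calculation, so slopes (0, 1), (0.5, 1.5) and (1, 2) must give the same answer.

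**Simulation.** Ordinary least squares with pooled residual variance, 21 per arm, 40,000 datasets per row. The last column is the share of datasets flagged at p<0.05 in which both within-arm slopes are significant at 0.05.

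| True slopes | g:t p<0.05 | g:t p<0.0001 | Both arms significant, among flagged |
|---|---|---|---|
| 0 and 1 | 83% | 14% | 4% |
| 0.5 and 1.5 | 83% | 14% | 50% |
| 1 and 2 | 83% | 14% | 96% |
| −0.75 and +0.75 | 99% | 59% | 74% |
| 0.5 and 0.5 | 5% | below 0.1% | (false positives) |

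The planned reading is true only in the first row, and the test cannot distinguish that row from the second and third. A stricter threshold does not help, because the null hypothesis is unchanged: among datasets flagged at 0.0001, both arms are significant in about 93% for slopes 1 and 2, and in 95% for −0.75 and +0.75.

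**Non-significance is not absence.** In the 0.5 and 1.5 row about half of the flagged datasets have only one significant arm, although both true slopes are non-zero. A slope with a large p-value therefore does not justify the word absent.

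**The case against.** The strongest reply is that this is a matter of wording with little downstream effect. Much of that stands.

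- **Pathway step.** It takes features from the linear models and needs no one-arm-only label. A pair whose slope truly differs by arm is a legitimate input.
- **Signature step.** Cross-validated classifiers work on the features, not on the verbal description. A reader might infer that the pathway results and the signature are corrupted. The documents do not support that, and nothing shows that pairs of different strength or opposite sign harm prediction.
- **Size.** Slopes of 1 and 2 with unit SDs mean within-arm correlations of about 0.71 and 0.89, which no document supports. With assumed slopes of 0.5 and 0.8 the term is significant in only about 15% of datasets at 0.05 and 0.1% at 0.0001. SAP item 2 also plans Benjamini–Hochberg control for omics data, so an unadjusted 0.05 may not be the operating threshold. The 83% is not a forecast error rate.
- **Breadth.** A reader might infer that any relationship present in both arms would be called arm-specific. That is not so: equal slopes are flagged only at the nominal rate.
- **A stricter remedy.** One could require the second arm's CI to lie within a margin around zero before calling a pair one-arm. With 21 per arm the 95% half-width is about 0.46 under unit SDs. Among flagged pairs with true slopes 0 and 1, margins of 0.3, 0.4 and 0.5 would retain under 1%, about 5 to 6% and about 23%. Limiting the signature to such pairs would also drop opposite-sign pairs, with no shown benefit.

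What does not stand is that the sentence is harmless. It is the stated rule of interpretation in both documents, and no other text requires anyone to look at the slopes.

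**Conclusion.** The interpretation rule is wrong as written. A significant g:t term supports a difference in slope and nothing more. Pairs with non-zero slopes in both arms that differ in size or sign would be described as existing in one arm only.

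The algebra needs no assumptions. The percentages rest on assumed slopes, unit SDs, 21 per arm and assumed thresholds. They show that the test cannot separate the cases, not how often the misdescription would occur; that cannot be computed from the documents.

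The consequence is confined to how individual pairs are described in the omics-integration analysis. Model 1 (follow-up on baseline and arm), the arm comparisons and the sample size are not affected.

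**What to change.** In SAP item 2 and protocol section 4.g.i, replace the sentence with: *a significant g:t term indicates that the gene (or miRNA or cytokine):metabolite slope differs between treatment groups.*

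Then add:

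- For each significant pair, report the slope and 95% CI in each arm from the same fitted model (b and b + d).
- Describe the pattern as same direction with different size, opposite direction, or clearly non-zero in one arm only. Do not claim absence in an arm merely because its slope is not significant.
- Let all g:t-significant pairs continue into the pathway and signature steps, described as treatment-dependent rather than treatment-specific.

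No equivalence margin is needed, and the signature need not be restricted to one-arm pairs. The cost is a few lines of text, slightly more reporting, and more modest claims about individual pairs. No new data or models are required.

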Untargeted metabolomic profiles: Metabolomics is an emerging technology that is being used to identify new biomarkers of tobacco smoke exposure (including by us) [147-155], and for studying COPD [156-158]. The assay assesses thousands of small molecules (< 1500 Daltons) that reflect exogenous exposures and cellular responses to those exposures. Metabolomics is now being widely applied to evaluate disease and disease causation [159-162]. In the case of smoking, metabolomic screening can reveal changes induced by cigarette smoke constituents as well as those due to endogenous cellular responses to cigarette smoke. We have published the usefulness of metabolomics for assessing smoke exposure in the blood and urine [147-149]. We have identified novel biomarkers related to smoking (e.g., glycerophospholipids and pathways related to inhibition of cAMP) that include some that differ by gender and race, and identified the presence of menthol metabolite}. We are not aware of metabolomics studies in the lung, but we also have demonstrated the feasibility for an untargeted metabolomics assessment for BAL (see below). Other studies suggest the utility for a BAL assessment, such as those that show changes in smokers' sputum [163], and for a bronchoscopy study for air pollution [164]. In an animal model, BAL metabolomics have mapped with emphysema progression, identifying a lung specific L-carnitine as a central metabolite [165].

Cytometry by Time of Flight (CyTOF) analysis: Using a mass spectrometry technique based on inductively coupled plasma spectrometry and time of flight mass spectrometry will determine the cellular expression, properties of cells (cytometry) to distinguish inflammatory cell subtypes.

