  - (1) Total and inflammatory cells: Total cell counts will be measured by 1:1 dilution in trypan blue and instillation into disposable Countess™ cell counting chamber slides [292]. Automated cell counts and viability will be evaluated by the Countess® Automated Cell Counter according to the manufacturer's instruction (Invitrogen, Carlsbad, CA). Differential counting will be performed on Diff-Quik stained cytopspins [293] and at least 200 cells will be counted on each preparation according to standard morphologic criteria under light microscopy. Differential cell counts will be evaluated by a histopathologist at OSUCCC.

- (2) Cellular component: Part of cells recovered from the BAL and nasal fluid will be lysed to measure expression of innate immune regulatory molecules. The remaining cells will be cultured up to 24h to determine their responsiveness to exogenous stimuli by quantitating newly released and newly produced intracellular molecules.
- (3) Cytokines: Inflammatory cytokines, TNF alpha and total protein concentration in the lavage fluid will be assessed using laboratory techniques including but not limited to MSD and ELISA assays, and cellular expression of these will be assessed on the cellular components by immunohistochemistry as previously described [294].
- (4) Glycerol and propylene glycol: Mass spectrometry methods. The assays will be developed and performed in the Nutrient Phytochemical Shared Resource of the OSUCCC, as previously described [182, 183, 290].
- (5) Untargeted metabolomics: mass spectrometry methods. These assays will be done in the Nutrient Phytochemical Shared Resource of the OSUCCC.
- (6) Cytometry by Time of Flight (CyTOF) analysis: Using a mass spectrometry technique based on inductively coupled plasma spectrometry and time of flight mass spectrometry will determine the cellular expression, properties of cells (cytometry) to distinguish inflammatory cell subtypes.
- (7) Tobacco use biomarkers: will be analyzed for validation of smoking cessation, the measurement of extent of tobacco use, and assessing exposure. This will include cotinine (metabolite of nicotine), nicotine, 3-hydroxycotinine, polycyclic aromatic hydrocarbons, NNAL (metabolite of tobacco-specific nitrosamines), anatabine and anasabine (tobacco alkaloids), mercapturic acids (metabolites of volatile organic compounds, and untargeted metabolomics.

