cytokines, and metabolites (resulting from the linear models) will be performed in Ingenuity Pathway Analysis to pinpoint altered pathways and better understand how the epigenomic/genomic/proteomic/environment affects metabolic phenotypes associated with e-cig usage. Furthermore, miRNA, genes, cytokines, and metabolites involved in treatment-specific associations will be used to predict treatment group, in an effort to produce an e-cig inflammation signature. Ten-fold cross-validations of various linear-based and non-linear based machine learning methods will be tried (e.g. Random forests, naïve Bayes, Lasso) and the resulting specificity and sensitivity will be assessed to select the best performing model. Of note, the cross-validation will help ensure that the predictive models are not overfit and could be predictive on new validation data. The contribution of input molecular measurements (gene, cytokines, miRNAs, metabolites) to the model will be assessed to define the minimal set of features that yield the optimal cross-validated models.

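### The exploratory e-cig inflammation signature is trained and selected only to predict arm, so exposure-derived metabolites that pass its screen could drive it without any inflammatory response

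*SAP*

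**What the plan says.** SAP item 2, repeated in Protocol 4.g.i, builds the signature in three steps.

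- **Screen.** The model is m = g + t + g:t, "where m are metabolite abundances, g are miRNA or gene or cytokine levels" and t is treatment group. The plan reads the interaction as follows: "A statistically significant g:t interaction p-value would indicate that gene (or miRNA or cytokine):metabolite relationships are present in one treatment group" and not in the other. No alpha or FDR level is given for this step, and g may be any miRNA, gene or cytokine.
- **Classifier.** In the SAP, miRNA, genes, cytokines and "metabolites involved in treatment-specific associations will be used to predict treatment group, in an effort to produce an e-cig inflammation signature". The Protocol states the same aim: "in an effort to produce an e-cig inflammation signature". Several machine-learning methods are tried with ten-fold cross-validation, and the best is picked on sensitivity and specificity.
- **Reduction.** The contribution of each input is assessed and the features are cut to a minimal set.

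On what the metabolite data contain, the Protocol's Background says: "The assay assesses thousands of small molecules (< 1500 Daltons) that reflect exogenous exposures and cellular responses to those exposures". Under Laboratory Procedures, the lavage list has an item "Tobacco use biomarkers: will be analyzed for validation of smoking cessation, the measurement of extent of tobacco use, and assessing exposure", and that item ends with "mercapturic acids (metabolites of volatile organic compounds, and untargeted metabolomics". Propylene glycol (PG) and glycerol have their own lavage assay, listed separately from untargeted metabolomics.

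The Protocol's follow-up bronchoscopy section tells participants in the two SREC arms to use their device immediately before that visit.

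**The concern.** The name of the output is not tied to what is optimised. The target is arm, selection is on arm prediction, and no step checks the score against an inflammatory endpoint such as lavage cell counts. Since the metabolite data are said to "reflect exogenous exposures and cellular responses to those exposures", a compound that came from the product or from tobacco is eligible if it passes the screen.

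Such a compound can pass without inflammation. If it is delivered in one arm only, its level varies with dose in that arm and sits at background in the other. Any gene that tracks dose will then correlate with it in one arm and not in the other, which is the pattern the screen seeks. The Protocol's Background itself reports dose-response mRNA changes with urine cotinine in 121 subjects, with xenobiotic-metabolism genes among the pathways implicated.

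Cross-validation protects against overfitting. It does not reveal a model that predicts arm correctly for the wrong reason. The reduction to a minimal set may also favour exposure compounds, because one of them can replace several weaker response markers. At stake is the reading of the result: a classifier of who used which product could be reported, in a study meant to inform regulation, as evidence about lung inflammation.

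**Working it through.** **Inputs from the documents.** 32 per group and 66% retention (SAP item 1); CV 0.5 for expression and metabolomics and a planning threshold of 0.0001 (SAP item 3). No performance figure for the signature is stated. No lavage fold change is given for any exposure compound. The nearest figure is urinary PG, which almost doubled in a cited trial of a 75% PG product (Protocol, Background); the SREC liquid is about 38.75% PG.

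**Plan's own figures.** 32 × 0.66 = 21.12, so 21 per group, and 21 × 4 = 84, as stated. With CV 0.5 the log-scale SD is √ln(1 + 0.5²) = 0.472. A two-sample t-test at two-sided 0.0001 with 21 per arm has 80% power at d = 1.613, that is a fold of exp(1.613 × 0.472) = 2.14, in line with the plan's 2.1. The conversion of CV to log SD is therefore consistent with the plan.

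**One exposure marker already in the model.** AUC = Φ(ln(fold) / (0.472 × √2)), with no biology.

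- 1.5-fold: Φ(0.405/0.668) = 0.73
- 2-fold: Φ(0.693/0.668) = 0.85
- 5-fold: Φ(1.609/0.668) = 0.99

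At CV 1.0 the 2-fold value falls to 0.72. These values ignore the screen.

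**Passing the screen through an unrelated g.** For k independent tests at p≤0.0001 the chance is 1 − (1 − 0.0001)^k: 9.5% for k = 1,000, 39% for 5,000 and 86% for 20,000. At p<0.05 it is essentially 100%. The unstated threshold therefore matters a great deal.

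**Screen plus classifier, simulated.** Assumed settings: 21 vs 21, CV 0.5, 50 metabolites of which 3 are exposure compounds, 1,000 g features, either none or 20 of them tracking dose, 100 runs per setting, and no arm effect on the mean of any gene or endogenous metabolite. Entries are mean cross-validated AUC.

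| Screen; gene-dose correlation | 1.5-fold | 2-fold | 3-fold | 5-fold | Exposure compounds removed |
|---|---|---|---|---|---|
| p≤0.0001; no gene tracks dose | 0.52 | 0.54 | 0.59 | 0.64 | 0.49–0.51 |
| p≤0.0001; 0.7 | 0.60 | 0.75 | 0.81 | 0.88 | 0.49–0.51 |
| Benjamini-Hochberg 5%; 0.9 | 0.66 | 0.81 | 0.92 | 0.96 | 0.42–0.46 |

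A given exposure metabolite entered in 8–13%, 42–51% and 26–31% of cases in the three rows. The third row averages only the 42 to 57 runs of 100 in which any feature passed. Under Benjamini-Hochberg 5% with correlation 0.7, entry was only 2–5% and any feature passed in just 11 to 16 runs, too few for a useful AUC.

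**The case against.** The strongest reply is that the screen does much of the work. A compound that is simply higher in one arm loads on t, not on g:t, so a mean shift alone does not admit it. A reader might infer that any untargeted metabolite may enter; the plan does not allow that. If the FDR control that the SAP applies to its 'omics tests were also applied here, entry would be uncommon unless genes track dose closely. This stands, and it is why the single-marker AUCs are not the right measure of size.

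Three further inferences are not supported:

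- **That PG and glycerol are in the untargeted matrix.** They have a separate lavage assay, and nothing says that the untargeted panel detects them.
- **That every contrast is affected alike.** Control smokers and the NRT and nicotine-SREC arms all have nicotine exposure, so nicotine products would mainly separate placebo SREC from the rest. PG and glycerol would not obviously separate the two SREC arms, since one carrier composition is listed.
- **That near-perfect classification is to be expected.** The 5-fold case has no basis in the documents.

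The plan also has partial safeguards. Inspecting each input's contribution would show an annotated exposure compound by name, and SAP item 2 already treats urine PG and tobacco alkaloids as exposure measures. But no rule says what follows if such a compound drives the model.

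**Conclusion.** The point holds as a limited one. As written, the procedure can return a classifier of exposure under the name of inflammation, and nothing planned is bound to detect it. With no biological arm effect and the screen applied, AUC is about 0.60 at a 1.5-fold and 0.75 at a 2-fold exposure contrast, against about 0.50 with exposure compounds removed. That rests on assumed settings (20 genes tracking dose at 0.7, p≤0.0001, CV 0.5). The range is wide: at 2-fold, 0.54 if no gene tracks dose and 0.81 under Benjamini-Hochberg with correlation 0.9 when anything passes.

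A reader might go further and conclude that the signature will be an exposure artefact. The documents do not show that: the lavage contrasts, the threshold and the content of the untargeted matrix are all unknown. Severity is low. The signature is exploratory, and the Model 1 arm comparisons in SAP item 3 do not depend on it.

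**What to change.** Amend SAP item 2 and the matching Protocol text in three respects.

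1. Before the g:t screen, remove metabolites annotated as product or tobacco constituents or their direct metabolites: nicotine and its metabolites, other tobacco alkaloids, flavourants, and PG and glycerol if the untargeted assay detects them. Fix the list in advance, and state the threshold for the screen.
2. Fit a classifier on the exposure compounds alone, in the same cross-validation folds, and report it beside the signature.
3. Call the result an inflammation signature only if it outperforms that comparator; otherwise call it an arm or exposure signature.

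The cost is an annotation filter, one more model run and some wording; no new samples or assays are needed. The price is lower reported accuracy. The filter is also incomplete, because unannotated features and genes that respond to xenobiotics may still carry exposure information. That is why the comparator is needed as well as the filter.
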